## Protocol Summary

- Full Title:** *Is it Feasible?: Self-Affirmation for Hereditary Breast and Ovarian Cancer Genetic Counseling*
- Principal Investigator:** *[name]*
- Sample Size:** *N= 74, patient control group =35, patient treatment group = 35, genetic counselors =4*
- Accrual Ceiling:** *180 participants*
- Study Population:** *Clients being seen for an initial visit in the hereditary breast and ovarian cancer (HBOC) clinic, both affected and unaffected with cancer, female, 18-90 years-old*
- Accrual Period:** *July 2017 – February 2017*
- Study Design:** *This study is a feasibility study to assess the acceptance and initial outcomes of a self-affirmation intervention in a novel HBOC genetic counseling context. The study relies on surveys of 4 genetic counselors and 70 clients after a small case control study. The purpose is to estimate effect sizes and preliminary outcomes of self-affirmation in a genetic counseling setting and to assess client and counselor interest in self-affirmation interventions.*
- Study Duration:** Start Date: *June 2017* End Date: *March 2017*
- Primary Objective:** *To identify outcomes that may be applicable for a larger SA intervention study in the genetic counseling context by randomly assigning clients to a control or intervention arm and then surveying them after the SA intervention and genetic counseling appointment.  
To assess clients' and counselors' opinions of an SA intervention by post study surveys.*
- Secondary Objectives:** *To assess process outcomes of a SA intervention including the time required to complete the intervention, uptake, and attrition.*
- Endpoints:** *Client's completion of follow-up survey; Counselor's completion of study review survey.*

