### **Feasibility study**

To our knowledge studies have not examined the impact of SA interventions in genetic counseling (Etchegary & Perrier, 2007). The ClinSeq study, designed to identify health-related genetic changes through exome sequencing, examined SA related to genetic risk perception and

information seeking. Although the ClinSeq study did not include a SA intervention, surveys did include assessments of participants' tendencies to engage in spontaneous SA.

Given the lack of evidence in this context it is important to conduct a feasibility study prior to a full-scale intervention to assess genetic counselors' and clients' reactions to the SA intervention, and the logistics of and barriers to SA implementation. Feasibility research studies generally have smaller sample sizes and therefore statistically significant outcomes are not expected. These studies allow for exploration of many aspects of implementation and preliminary outcomes. The National Cancer Institute has recognized the need for more intervention-based feasibility studies prior to full-scale studies to determine "whether comprehensive and multilevel evaluations are justified (Bowen et al., 2009, p. 1)." A feasibility study of SA in genetic counseling would allow for preliminary examination of the impact of SA on genetic counseling session outcomes to provide estimates of effect size, confidence intervals and, consequently, necessary sample size for a future study.

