## **6.0 Description of study population**

#### 6.1 Estimated number of participants, enrollment ceiling, and anticipated enrollment by year.

The client participants will be female patients being seen at the high-risk breast and ovarian cancer clinic at St. Luke's Health System and Medstar Washington Hospital Center, for their initial appointment for genetic counseling for HBOC. Participant selection will be indiscriminant of if they have cancer or if they have already had genetic testing through another provider. Participants must be at least 18 years of age. For a fully powered study of the effect of self-affirmation on genetic counseling outcomes, we estimate that we would need 296 participants to identify a small to medium effect (Cohen's  $d = 0.35$ ) with beta being 0.85 and alpha being 0.05. This Cohen's  $d$  is based on other SA interventions in the education and emerging medical literature. For this feasibility study we seek to recruit 70 client participants and 4 genetic counselor participants. We chose this number for several reasons. The genetic counselors at St. Luke's Health System see about 40 new patients a month. Over the 4 months of data collection there will be 180 appointments. We believe that getting 70 of these clients to consent is an achievable estimation. Additionally, feasibility studies typically range from 30-50 participants to estimate attrition and confidence intervals. The enrolment ceiling is 180 participants. Genetic counselor participants two genetic counselors at the St. Luke's health system HBOC clinic. Participants will be enrolled by February of 2018. To this point, we have been recruiting about 8 patients a month instead of expected 17 through St. Luke's Health System. To our knowledge, this is because the counselors are seeing more colorectal and other cancer patients than expected instead of HBOC patients and we have been able to reach less patients for consent. About half decline to be contacted and 1/3 cannot be reached by the AI for consent. For this reason, we are adding the Medstar Washington Hospital Center site and extending the recruitment window. Genetic counselor participants are two genetic counselors employed in the HBOC genetic counseling clinic at St. Luke's Hospital and two genetic counselors who see HBOC patients at Medstar Washington Hospital Center.

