## **7.0 Description of study statistical considerations and/or analytic plan:**

*Aims have been copied here for ease of interpretation.*

Aim 1: To assess the preliminary impact of a novel SA intervention on outcomes that may be targeted in future studies, by assessing differences in the following between a SA intervention and unaffirmed standard SA intervention control group of HBOC genetic counseling clients:

- a. Intentions to talk with family, test uptake
- b. Empowerment, decision self-efficacy
- c. HBOC knowledge

The primary goal of analysis of aim 1 is to identify which outcomes would be most appropriate for follow up studies and the necessary sample size for adequate statistical power.

For decision efficacy, the scores on the Decision Self-Efficacy Scale (See section 2 of client survey, Appendix D) will be compared between groups using linear regression controlling for education, race, anxiety score, and effectiveness of intervention (based on last question on intervention Appendix C). Intention to talk with family, genetic testing uptake, and information seeking will be measured similarly using linear regression.

Client empowerment will be analyzed by using the GCOS-24 a 24-item likert scale completed by clients and parallel scale by genetic counselors (See section 3 of client survey of appendix D and appendix F). Both scales will be compared between groups using linear regression controlling for education, race, anxiety score, and effectiveness of intervention (based on last question on survey). Discrepancies between counselor and client surveys will be analyzed using dyadic analyses. For this analysis, we will assess the correlation between paired client and genetic counselor GCOS-24 for the compete survey and for the individual questions.

HBOC knowledge will be analyzed between groups using linear regression testing the knowledge scale (See section 4 of client survey, Appendix D) and controlling for education, race, anxiety score, and effectiveness of intervention.

Effect sizes and standard deviations for each outcome will be identified, and an estimated sample size for a fully powered study will be estimated based on power calculations.

Aim 2: To describe genetic counselors' (GCs) and clients' response to a novel, client-based SA intervention, including perceived impact, barriers, and facilitators to implementing such an intervention on a wider scale

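### Section 7.0 takes the follow-up trial's sample size from the pilot's own effect estimates without saying which effect enters the power calculation; at 35 per arm the observed effect is too noisy for that use

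*Combined protocol and SAP*

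**What the plan says.** Section 7.0 gives the primary goal of the Aim 1 analysis as to "identify which outcomes would be most appropriate for follow up studies and the necessary sample size for adequate statistical power". The method for the second half of that goal is one sentence: "Effect sizes and standard deviations for each outcome will be identified, and an estimated sample size for a fully powered study will be estimated", with power calculations named as the basis.

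Section 3.0, under Feasibility study, makes the link more directly. The pilot is to "provide estimates of effect size, confidence intervals and, consequently, necessary sample size for a future study".

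Section 6.1 already holds a separate plan: "we would need 296 participants to identify a small to medium effect", at Cohen's d = 0.35, and that value "is based on other SA interventions in the education and emerging medical literature". Section 3.0 also cites a meta-analysis with d = 0.26 for health intentions and 0.27 for behaviors, and argues that the effect in this population should be larger.

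No section says how the pilot estimate is to be combined with, or checked against, d = 0.35 and N = 296. Section 7.0 describes seven between-arm comparisons (decision self-efficacy, family intention, test uptake, information seeking, client GCOS-24, counselor GCOS-24, knowledge). It gives no grounds for judging one of them more suitable than another.

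**The concern.** The follow-up sample size is a stated product of Aim 1, so the method that yields it should be fit for the purpose. Required N varies with 1/d², so error in an estimated d is magnified when it is turned into a sample size. With 35 per arm, a power calculation at the observed d can call for a trial far too small or far larger than needed, and the pilot gives no sign of which has happened.

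Outcome choice could add to this. If the outcome with the largest observed effect is carried forward, which section 7.0 does not exclude, the effect used for planning is biased upward as well as noisy.

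What is at stake is the size of a later trial. That trial can still write its own justification.

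**Working it through.** **Inputs.** From the documents: 35 clients per arm (section 5.0); d = 0.35, alpha 0.05 and N = 296 (section 6.1); d = 0.26 (section 3.0). Section 6.1 labels 0.85 as beta; it is read here as power. Assumed: two-sided test, one prespecified continuous outcome, no covariates, no attrition, and planning at the observed d or at its lower 95% limit.

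**1. The plan's own figure.** Per arm, n = 2 × ((1.96 + 1.036)/d)² + 1.96²/4, rounded up.
- d = 0.35: 2 × (2.996/0.35)² + 0.96 = 147.5, so 148 per arm and 296 in total. The stated figure reproduces, and an exact t-test calculation agrees.
- d = 0.26: 2 × (2.996/0.26)² + 0.96 = 266.5, so 267 per arm and 534 in total.

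**2. Precision of the pilot.** SE(d) = √(2/35 + 0.35²/136) = √(0.0571 + 0.0009) = 0.241. An observed d of 0.35 has a 95% interval of 0.35 ± 1.96 × 0.241, or −0.12 to 0.82.

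**3. What that does to N.** Take an observed d about one standard error either side of 0.35.
- d = 0.59: 2 × (2.996/0.59)² + 0.96 = 52.5, so 53 per arm, N = 106.
- d = 0.11: 2 × (2.996/0.11)² + 0.96 = 1,484.6, so 1,485 per arm, N = 2,970.

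**4. Simulation.** 400,000 pilots per true effect, 35 per arm, normal outcome. N is planned at the observed d for 85% power, and true power is then evaluated at the true d. Rows on N and power refer to pilots with d above 0.

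| | True d = 0.35 | True d = 0.26 |
|---|---|---|
| Observed d at or below 0 (no N) | 7% | 14% |
| Middle half of planned N | about 130 to 700 | about 180 to 1,230 |
| N needed | 296 | 534 |
| True power, mean / median | 74% / 81% | 68% / 73% |
| True power below 50% | 24% | 33% |
| Lower 95% limit at or below 0 (all pilots) | 70% | 81% |

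For one prespecified outcome this is noise and not bias: at true d = 0.35 the mean observed d is 0.353, and the planned N is too small in about 50% of pilots.

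**5. Sensitivity.**
- With 30 or 25 analysable per arm (assumed), SE(d) is about 0.26 or 0.28.
- If covariates explained half the variance (assumed R² = 0.5), SE(d) would be about 0.17 and the half-width 1.96 × 0.17 = 0.33, still nearly as large as 0.35 itself.
- If seven outcomes all had true d = 0.35 and the largest observed effect were chosen, its expected value would be about 0.49 (correlation 0.8, assumed) to 0.67 (correlation 0).

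**The case against.** The documents do not claim more than a pilot can deliver on testing: "Feasibility research studies generally have smaller sample sizes and therefore statistically significant outcomes are not expected". They list confidence intervals as an output and hold a literature-based plan in section 6.1. Nowhere do they say that the point estimate will be used mechanically, so the simulation tests an assumed rule. It also models an unadjusted comparison, whereas section 7.0 plans adjusted regressions, and test uptake is a yes/no outcome. How far pilot effects should inform a later trial is partly a matter of preference.

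Much of this stands, and it limits the point. It does not remove it. The statement about significance concerns tests within this study and gives no rule for carrying the same imprecision into the next trial's N. The intervals are named, but their use is not.

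A reader might go further in four ways that the documents do not support.
- *The pilot is at fault because it cannot tell N = 296 from N = 534.* Its 95% interval does cover both 0.26 and 0.35 in about 92% of runs, but so does that of a 296-person trial in about 86%. The test is not specific to this study.
- *The follow-up should be planned at d = 0.26.* Section 3.0 notes that 12 of the 16 studies used student samples with distant or impersonal threats, and expects a larger effect here. N = 534 appears nowhere in the documents.
- *N = 296 is wrong.* It reproduces from its own inputs.
- *The Protocol Summary makes the same error.* It says "The purpose is to estimate effect sizes and preliminary outcomes of self-affirmation in a genetic counseling setting" and makes no claim about sample size.

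**Conclusion.** The point holds as a minor one. Section 7.0, read with the Feasibility study text in section 3.0, derives the follow-up sample size from the pilot's effect estimates, leaves the planning value unstated, and does not connect it to section 6.1. On the most direct reading, at the protocol's own d = 0.35, the method gives no N in about 7% of pilots. In the rest it yields mean true power of about 74%, with roughly one follow-up in four below 50%. The lower-limit alternative usually gives no finite N.

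These figures rest on planning at the observed d or its lower limit, which the documents do not state, and on one unadjusted continuous outcome without attrition. They are only illustrative for the adjusted regressions and for test uptake. No participant and no estimate in this study is affected.

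**What to change.** Replace the sample-size sentence at the end of Aim 1 in section 7.0 with wording such as:

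> Pilot effect sizes will be reported with 95% confidence intervals as descriptive results. The follow-up sample size will not be set from the pilot point estimate alone. It will be computed at a target effect named and justified before between-arm results are seen, and shown over a range that includes the d = 0.35 of section 6.1 and, as a sensitivity case, the meta-analytic d = 0.26, with the power each N keeps across that range. Pilot attrition will inflate N. Pilot standard deviations will be used where the target is stated in raw scale units. For test uptake, the control-arm proportion will be used, with the target stated as a difference in proportions. Candidate outcomes will be judged on prespecified grounds (relevance, completeness, floor and ceiling effects, variability) and not on the observed effect alone.

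The distinction over standard deviations matters: when the target is a standardized d, the SD drops out of the calculation. In section 3.0, Feasibility study, change the wording that makes the sample size a consequence of the pilot effect estimate. The Protocol Summary needs no edit, and the choice of target stays with the study team.

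The cost is wording in two places, with no change to data collection. The downside is that the pilot no longer supplies a single data-driven N, and a fixed target can also be wrong: N = 296 has 85% power at d = 0.35 but 61% at d = 0.26, while N = 534 has 98% and 85%. That is why the range should be shown.

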### Specific aims

1. To assess the preliminary impact of a SA intervention on outcomes that may be implemented in future studies, by assessing differences in the following between a SA intervention and unaffirmed standard SA control group of HBOC genetic counseling clients:
  - a. Intentions to talk with family, test uptake
  - b. Empowerment, decision self-efficacy
  - c. HBOC knowledge
2. To describe genetic counselors' (GCs) and clients' response to a novel, client-based SA intervention, including perceived impact, barriers, and facilitators to implementing such an intervention on a wider scale

3. To assess the percentage of eligible clients that completed a pre-visit SA intervention and if the SA intervention is effective in affirming clients.

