#### **5.0 Description of procedures:**

In this intervention-based randomized controlled feasibility study, Hereditary Breast and Ovarian Cancer (HBOC) genetic counseling clients will receive an intervention and short survey before their appointment and will complete a survey after their appointment. Genetic counselors who counsel participating clients will complete a post-appointment survey after each appointment with a participating client and a survey at the end of the study.

Thirty-five client participants will be randomly assigned to complete the self-affirmation intervention and 35 participants will complete the control condition. Client participants will be patients being seen for an initial appointment for genetic counseling at the HBOC genetic counseling clinic, regardless of current cancer status. All client participants will take a state anxiety measure before their appointment to control for some of the variability in indication. Client participants will also indicate if they have cancer, if they have received genetic testing, and if they were offered genetic testing at the current visit. Genetic counseling can be indicated for patients without cancer who have a family history of cancer, for patients with cancer, and for self-referred patients who are concerned about their cancer risk. Most often, the initial cancer genetic counseling appointment occurs before qualification for genetic testing is assessed and clients have a follow-up appointment to receive results. Sometimes oncologists or primary care physicians order genetic tests and the initial genetic counseling appointment includes results delivery and education. Any client with an initial genetic counseling appointment will be invited to participate in the study. Follow-up appointments will not be included because patients already have a relationship with the genetic counselor. The four genetic counselors, who have appointments with the participating clients, will be enrolled in the study as genetic counselor participants.

The SA intervention consists of participants ranking 11 items (artistic skills, athletics, business/money, creativity, independence, music, politics, relationships with friends and family, religious values, sense of humor, spontaneity) from most important to least important (See

[figure not shown]

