This aim will be analyzed as percent of yes/no response to intervention survey questions for both clients and counselors. There will also be open ended questions for specific impacts, barriers, and facilitators to be mentioned, which will be analyzed using thematic analysis of answers. The AI will create a codebook based on initial read through and subsequently code all answers. A separate coder will validate ten percent of answers for consistency.

Aim 3: To assess the percentage of clients that completed a pre-visit SA intervention among client participants and if the SA intervention is affective in affirming clients.

Intervention uptake will be reported as a percentage of participants who were eligible based on counselor referral and who were contacted by AI that completed the SA intervention and client survey. Effectiveness of affirmation is an internal control and will be assessed by screening the last question on the intervention for those in the intervention group who report higher than a 2 and those in the control group who report lower than a 5. Additionally, transcripts of intervention essays will be analyzed for affirmation themes.

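### Aim 3 uptake has three different denominators; the planned one omits clients who refuse the permission call, and the planned numerator mixes uptake with survey return

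*Combined protocol and SAP*

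**What the plan says.** The third specific aim in section 2.0 begins "To assess the percentage of eligible clients that completed a pre-visit SA intervention". Section 7.0 says that it repeats the aims for convenience, but words this one differently: "To assess the percentage of clients that completed a pre-visit SA intervention among client participants". The analysis sentence below it brings in another base, "Intervention uptake will be reported as a percentage of participants who were eligible based on counselor referral and who were contacted by AI", and counts those "that completed the SA intervention and client survey". It does not say whether contacted means that a call was attempted or that the client was reached.

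The secondary objective in the Protocol Summary is "To assess process outcomes of a SA intervention including the time required to complete the intervention, uptake, and attrition", so uptake and attrition are named as distinct outcomes. Section 7.0 gives no formula for attrition and no percentage for task completion alone.

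Under section 6.4, clinic staff at both sites first ask clients whether they will accept a call about the study. Only those who agree are telephoned by the associate investigator. Section 6.1 reports, for recruitment through St. Luke's: "About half decline to be contacted and 1/3 cannot be reached by the AI for consent". Section 5.0 places the survey after the appointment. It can be returned at the desk, by mail or online, with a reminder a week later.

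**The concern.** The trial's stated objective is feasibility, and this is one of its three specific aims. Two features of the planned percentage keep it from answering the aim in section 2.0.

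- **Denominator.** It begins after the permission call, so it omits a large early loss that the protocol itself reports.
- **Numerator.** Read plainly, it counts only clients who did both the task and the survey. A low value could mean that clients would not do the writing task or that they did not return a questionnaire afterwards. Those two problems need different remedies in a larger study.

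A team planning that study could take the figure as uptake among eligible clients, which it is not.

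**Working it through.** The plan states no expected uptake or attrition, so there is no figure of its own to reproduce. The check traces clients from identification to survey.

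**Inputs from section 6.1 (St. Luke's, approximate, bases not stated):** about 1/2 decline contact; 1/3 cannot be reached; about 8 clients recruited a month. Appointments are given as about 40 a month, and also as "Over the 4 months of data collection there will be 180 appointments", which is 180/4 = 45 a month. Both are carried below.

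**Notation.** Let x be the share of eligible clients who complete the task, r the share of eligible clients in the planned denominator, and s the survey return among task completers (not in the documents).

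- Section 2.0 quantity = x
- Planned figure = x·s / r
- Ratio of planned figure to section 2.0 quantity = s / r

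**Denominator alone (s = 1):**
- Contacted means attempted: r = 1 − 1/2 = 0.50, so 1/r = 2.0.
- Contacted means reached, with the 1/3 taken among those who agreed to a call: r = 1/2 × 2/3 = 0.333, so 1/r = 3.0.

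**Adding the survey condition.** The two departures cancel when s = r, that is at 50% (attempted) or 33% (reached). Above that value the planned figure is higher than the section 2.0 quantity; below it, lower. If s is assumed to lie between 50% and 100%, the ratio is 1.0 to 2.0 (attempted) or 1.5 to 3.0 (reached).

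**Against the section 7.0 wording.** Let c be the share of contacted clients who become participants and t the task completion among participants. The restated aim is t and the planned figure is c·t·s, so the ratio is c·s, which cannot exceed 1. Here the planned denominator is the broader one.

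**Illustration (assumed: consent 80% of those reached, task 90%, survey 80%):**
- Section 2.0 aim: 0.333 × 0.8 × 0.9 = 24.0%
- Restated aim: 90%
- Planned figure, reached: 0.8 × 0.9 × 0.8 = 57.6%
- Planned figure, attempted: 57.6% × 0.333/0.50 = 38.4%

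**Merging of uptake and attrition.** If all contacted clients consent, 90% task completion with 60% survey return gives 54%, and 60% with 90% also gives 54%.

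**The case against.** Several points on the other side have force.

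- **The numerator wording is loose.** It could mean two percentages, one for each instrument. That stands as a possible reading, although the sentence speaks of a single percentage. It would not cure the denominator.
- **A contacted-client base is partly defensible.** Section 6.2 requires English literacy and capacity to consent, which the schedule may not show. A schedule-based denominator is therefore only apparently eligible. This supports keeping the contacted-client percentage as a second figure, but not as the only one.
- **The data may allow separation.** Task forms and surveys are separate documents linked by code word (section 10.0). A reader might infer that the study cannot distinguish uptake from attrition. The documents do not support that: the limitation lies in the planned percentage and the missing reporting rule. A count that needs both forms could, however, also fall through failed matching, because section 10.3 excludes documents that cannot be linked.
- **The loss rates come from St. Luke's only.** Medstar, expected to supply about 16 of 70 clients (section 5.0), has no data, so the rates should not be applied to both sites.
- **Section 5.0's statement** "Any client with an initial genetic counseling appointment will be invited to participate in the study" might seem to contradict the permission step. It is compatible with the information leaflet that section 6.4 says goes to all clients, so nothing rests on it.

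A reader might also take the unreachable 1/3 as a share of all clients, giving r = 1/2 − 1/3 = 1/6 and a 6-fold effect. That would mean 45/6 = 7.5 or 40/6 = 6.7 clients reached a month, fewer than the roughly 8 recruited, and so a consent rate of 107% to 120%. Section 6.1 also says that fewer HBOC patients were seen than expected, which makes this reading less tenable still. The 3-fold reading passes the same check: 15 or 13.3 reached, so 53% to 60% consent.

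**Conclusion.** The point holds as an inconsistency of definition. One aim has three denominators, and the one chosen for analysis excludes clients who decline the permission call on either meaning of contacted. Relative to section 2.0, the denominator alone raises the percentage about 2-fold (attempted) or 3-fold (reached). This rests on approximate St. Luke's rates, with the 1/3 taken among those who agreed to a call.

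A reader might conclude that the plan will overstate uptake. That is not established: the survey condition pulls the other way by an unknown amount, and against the section 7.0 wording the planned figure cannot exceed the aim quantity. What can be said is that the figure does not measure uptake among eligible clients and, read plainly, does not separate uptake from attrition.

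The percentage is descriptive, with no target attached, and the between-arm comparisons of Aim 1 do not depend on it. It should still be fixed, because it is a main feasibility result and the early-step counts have to be kept while recruitment runs.

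**What to change.** 1. Use one wording of Aim 3 in sections 2.0 and 7.0.
2. Define uptake as completion of the assigned pre-visit writing task, self-affirmation or control, divided by all clients identified on the schedule as apparently eligible.
3. Report survey return among task completers separately, as attrition.
4. Keep the percentage among contacted clients as a labelled secondary figure, with contacted defined as attempted or reached.
5. Reconcile eligibility by counselor referral (section 7.0) with identification by the scheduling coordinator at St. Luke's (section 6.4).
6. Report counts by site: identified, agreed to contact, reached, consented, task completed, survey returned.

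The cost is plan wording and a simple anonymous tally at both sites. Section 6.1 suggests that declines and non-reach were already being followed, at least roughly, at St. Luke's. Medstar has no single coordinator, so someone there must be named to keep the tally. The denominator will be only apparently eligible clients, and the reported uptake will probably be lower.

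### Aim 3 asks whether the self-affirmation task affirms clients, but the affirmation item is only screened within each arm on different cut-offs and is never compared between the randomised arms

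*Combined protocol and SAP*

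**What the plan says.** Specific aim 3 in Section 2.0 includes finding out "if the SA intervention is effective in affirming clients", and Section 7.0 restates the question under Aim 3. The method given there is: "Effectiveness of affirmation is an internal control and will be assessed by screening the last question on the intervention". The screen picks out "those in the intervention group who report higher than a 2 and those in the control group who report lower than a 5". As a second check, "transcripts of intervention essays will be analyzed for affirmation themes"; no comparison of themes by arm is described.

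The item's other use is in the Aim 1 regressions, which adjust for "effectiveness of intervention (based on last question on intervention Appendix C"). The outcomes compared between groups there are decision self-efficacy, the client and counselor GCOS-24, HBOC knowledge, intention to talk with family, testing uptake and information seeking. The affirmation item is not among them.

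On design, Section 5.0 states: "Thirty-five client participants will be randomly assigned to complete the self-affirmation intervention and 35 participants will complete the control condition". The stated goal of the Aim 1 analysis is to "identify which outcomes would be most appropriate for follow up studies and the necessary sample size for adequate statistical power".

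**The concern.** The control arm does a parallel writing task, so whether the self-affirmation task affirms clients is naturally a question about one arm against the other. The plan instead produces two within-arm counts, each on its own cut-off. Neither count says how far the task moved affirmation relative to the control task, and the two together do not say so either.

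Two things are at stake. First, part of a stated aim ends without an estimate. Second, the gap affects how Aim 1 is read. If an outcome shows little difference between arms, it may be unresponsive to affirmation, or the task may not have affirmed clients more than the control task did. The between-arm difference in the item is the direct quantitative evidence on which of these applies, and it bears on which outcomes go forward to a larger study.

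**Working it through.** **Inputs.** The cut-offs (above 2 in the intervention arm, below 5 in the control arm) and the covariate role come from Section 7.0. The 35 per arm comes from Section 5.0. Whole-number answers are assumed. The item's wording, range and direction are in Appendix C, which was not available for this review; that is not a fault of the plan. The plan gives no expected value, SD or target for this item, so it has no figure to reproduce here. Its one sample-size figure, 296 in Section 6.1, concerns counseling outcomes.

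**Step 1: is there any between-arm analysis of the item?** Set side by side, the Aim 3 text screens the item within each arm and analyses essays for themes, while the Aim 1 text enters the item on the right-hand side of the regressions. A covariate's coefficient describes how the item relates to an outcome. It does not describe how assignment changed the item. No between-arm comparison is stated.

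**Step 2: can the two screened shares stand in for one?** Above 2 means 3 or more, and below 5 means 4 or less. Answers of 3 and 4 therefore satisfy both criteria. Suppose both arms answer identically, so there is no effect, with answers spread evenly over an assumed scale:

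| Assumed scale | Share above 2 | Share below 5 |
|---|---|---|
| 1 to 5 | 3/5 = 60% | 4/5 = 80% |
| 1 to 6 | 4/6 = 67% | 4/6 = 67% |
| 1 to 7 | 5/7 = 71% | 4/7 = 57% |

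With zero effect the two shares can be equal, or either can be the larger.

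**Step 3: does the direction of the scale matter?** Write I and C for the arms and X for the answer. As an illustration only, suppose someone took each arm's share affirmed from its own cut-off and subtracted.

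- If high means affirmed: P_I(X≥3) − P_C(X≥5) = [P_I(X≥3) − P_C(X≥3)] + P_C(X = 3 or 4).
- If low means affirmed: P_I(X≤2) − P_C(X≤4) = [P_I(X≤2) − P_C(X≤2)] − P_C(X = 3 or 4).

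The bracket is the difference on a common cut-off between 2 and 3. The own-cut-off figure misses it by the control-arm share answering 3 or 4, upward in the first case and downward in the second. With no effect and an assumed 30% answering 3 or 4, the gap would be +30 or −30 points. The shares fail as an estimate in both directions.

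**Step 4: precision of a direct comparison.** The 95% half-width in SD units, without covariates, is t(0.975, 2n−2) × √(2/n). For a difference in percentages near 50% on one common cut-off it is 1.96 × √(2 × 0.25/n).

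| n per arm | Half-width, item score | Half-width, percentages |
|---|---|---|
| 35 (planned) | 0.48 SD | 23.4 points |
| 30 (assumed) | 0.52 SD | 25.3 points |
| 25 (assumed) | 0.57 SD | 27.7 points |
| 20 (assumed) | 0.64 SD | 31.0 points |

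**The case against.** The strongest reply has four parts.

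*The item may not be the same in both arms.* Intervention clients write about their top-ranked value, and controls write about their ninth-ranked item and why it might matter to someone else. If the last question refers to what was written, arm-specific cut-offs could be deliberate and a raw difference could largely reflect the assigned topic. This is mostly answered by Section 7.0, which names a single last question and enters it as one covariate across both arms. Because Appendix C could not be checked, the fix should be conditional. Section 7.0 also gives the source of the effectiveness covariate as the last question on the survey in the GCOS-24 paragraph, and as the last question on the intervention elsewhere; this should be clarified at the same time.

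*It is only an internal control.* A per-client check is legitimate and should stay. But effectiveness in affirming clients is part of a specific aim, and this check is its only quantitative analysis.

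*This is a feasibility study.* Section 3.0 says statistically significant outcomes are not expected. It also says the study should provide effect sizes and confidence intervals, which is what is asked for here.

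*The added estimate would be imprecise.* This stands. At 35 per arm a two-sided 5% test would have 80% power only for a difference of about 0.68 SD, so the interval will only partly separate an unresponsive outcome from a task that did not affirm.

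A reader might also infer that the plan will report an affirmation effect wrong by a known number of points, or will declare success when most of each arm passes. The documents support neither. They state no subtraction of shares and no majority rule, so the Step 3 figures describe a possible misuse and not a planned analysis. Nor do the documents say what happens to clients picked out by the screen, so exclusion from analysis should not be assumed.

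**Conclusion.** The concern holds as a gap in the analysis for Aim 3. Followed as written, the plan gives no quantitative estimate of affirmation in the intervention arm against the randomised control. The overlap at 3 and 4 means the two screened shares cannot supply one, whichever way the scale runs. This rests on the text of Section 7.0 and on whole-number answers; it does not depend on scale length or on any distribution.

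The consequence is moderate. The missing comparison biases no planned estimate. If the item is common to both arms, the difference can be calculated from data already being collected. A reader might infer that Aim 1 cannot be interpreted without it. That goes too far: at about ±0.48 SD with 35 per arm, or ±0.57 SD with 25, the estimate would inform the reading of small Aim 1 differences without settling it. The change is still worth making, because a stated aim should have its own estimate.

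**What to change.** First confirm from Appendix C that the item and its coding are the same in both arms. State in Section 7.0 the scale's direction and whether the screen counts clients who passed the check or who failed it.

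If the item is the same, add to Section 7.0, as the main answer to the effectiveness part of Aim 3, the between-arm difference in the item (intervention minus control) with its 95% confidence interval. Analyse by assigned arm, in all randomised clients who answered the item. If a percentage affirmed is reported, apply one common cut-off in both arms and give the difference with its 95% interval. Keep the existing screen and the essay themes as descriptive checks. If Appendix C shows that the item differs by arm, say so, and describe the screen as a within-arm check that does not estimate the effect of the task.

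The cost is a few sentences and one descriptive analysis. No new data are needed if the item is common to both arms, since Section 7.0 already sets a cut-off for each. The drawback is a wide interval, which should be presented as an estimate and not as a test.
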